6.7 Study Treatment Non-Compliance and Dosing Errors

Treatment non-compliance and dosing errors for reasons other than AE will be summarized for subjects in the Safety population. Frequency counts and percentages will be presented by treatment arms for:

- Subjects with dose hold (0 mg) due to subject non-compliance, site/logistic error or other reason
- Subjects who overdosed (received dose > maximum allowed dose level) at any time due to subject non-compliance, site/logistic error or other reason
- Subjects who received non-protocol specified dose level (< maximum allowed dose level) at any time due to subject non-compliance, site/logistic error or other reason

Subjects who received study treatment not randomized to

6.8 Concomitant and Subsequent Non-protocol Non-radiation Anti-cancer Therapy

For the purpose of supporting safety evaluation:

Concomitant and subsequent non-protocol non-radiation anti-cancer therapies including radionuclides, will be summarized by ATC text and WHO-DD base substance preferred name by therapy type in the ITT and Safety populations. Based on the systemic therapy received, subjects will also be grouped by special categories into one or more of the following:

- Systemic non-radiation anti-cancer therapies
 - Cytotoxic agents
 - o Multi tyrosine kinase inhibitors (TKI) (without RET inhibitor activity)
 - o Multi tyrosine kinase inhibitors (TKI) (with RET inhibitor activity)
 - RET-specific inhibitors
 - Immunotherapy (PD-1/PD-L1/CTLA4/Other)
 - Other systemic therapies

6.9 Post-randomization Radiation, and Surgery/Procedure

For the purpose of supporting efficacy evaluation:

Post-randomization radiation therapy, surgery/procedure will be summarized for all subjects in the ITT population in one consolidated table. Frequency counts and percentages will be presented by treatment groups for:

Radiation

- Number of subjects who received any radiation therapy
- o Therapy indication
- Site by MTC vs. other than MTC indications
- Number of subjects who received radiation other than radiation to bone
- Surgery/procedure
 - o Number of subjects who received any surgery/procedure related to MTC

7 EFFICACY ANALYSES

Unless otherwise indicated, all efficacy analyses will include all subjects in the ITT population.

7.1 Primary Efficacy Endpoint

The primary efficacy endpoint is duration of PFS as determined by the IRC.

7.1.1 Definition

Progression-free survival is defined as the time from randomization to the earlier of either progressive disease per IRC per RECIST 1.1 or death due to any cause.

PFS per IRC (months) = (earliest date of progression per IRC, death, censoring – date of randomization + 1)/30.4375

7.1.2 Statistical Objective

The goal of the study is to establish that treatment with cabozantinib at 60 mg is non-inferior to treatment with cabozantinib at 140 mg as defined by retaining 50% of the treatment effect of cabozantinib at 140 mg as measured by PFS.

Non-inferiority will be concluded if the upper 95% CI for the HR (cabozantinib 60 mg/140 mg) is less than the non-inferiority margin of 1.58.

7.1.3 Primary Analysis

The primary efficacy analysis of PFS will include all subjects in the ITT population and will evaluate whether PFS for subjects in the 60 mg cabozantinib arm is non-inferior to PFS in subjects in the 140 mg cabozantinib arm. The primary efficacy analysis is event based and will be conducted when at least 150 PFS events have been observed.

The recorded date of radiographic progression is the date of the tumor assessment visit at which progression is declared per IRC per RECIST 1.1. If multiple scan dates are associated with a tumor assessment visit, the earliest assessment date within the set will be chosen as the progression date.

Only adequate tumor assessments (ATAs) will be considered in the determination of radiographic progression and censoring dates. For the purpose of this study, ATA is defined as one that results in a time point assignment of: response (complete or partial), stable disease/(non-

CR, non-PD), or progression. For PFS, ATA is based on soft tissue evaluation by CT/MRI.

Single missing or inadequate scheduled tumor assessments will be ignored. No values will be imputed.

The censoring rules shown in Table 3 will be applied to the primary and sensitivity analyses of PFS.

Table 3: Censoring Rules for Analyses of Progression Free Survival

Туре		PFS-A1		PFS-B1	
Analysis	Primary		Primary		
Radiographic PD per		IRC	Investigator		
Population		ITT		ITT	
Condition	Outcome	Date of Outcome	Outcome	Date of Outcome	
No post-baseline ATA	Censored	Date of randomization	Censored	Date of randomization	
Death	Event	Date of death	Event	Date of death	
Radiographic soft-tissue PD	Event	Date of PD	Event	Date of PD	
Clinical deterioration	NA	NA	NA	NA	
Any systemic non-protocol anti- cancer therapy (NPACT) received on or after randomization date	Censored	Date of last ATA on or prior to initiation of therapy	Censored	Date of last ATA on or prior to initiation of therapy	
Radiation (other than to bone)	Censored	Date of last ATA on or prior to radiation	Censored	Date of last ATA on or prior to radiation	
Surgery impacting soft tissue lesions	Censored	Date of last ATA on or prior to surgery	Censored	Date of last ATA on or prior to surgery	
≥ 2 consecutive missing scheduled ATA immediately prior to rPD or death	Censored	Date of last ATA prior to the missing assessments.	Censored	Date of last ATA prior to the missing assessments.	
None of the above	Censored	Most recent of: the date of last ATA or randomization.	Censored	Most recent of: the date of last ATA or randomization.	

ATA=Adequate Tumor Assessment; PD=Progressive Disease; NA=Not Applicable; rPD = radiographic PD; RT=Radiotherapy Two or more missed scheduled ATA is operationally defined as >178 days without an evaluation

Table 3: Censoring Rules for Analyses of Progression Free Survival (continued)

Туре	PFS-A2		PFS-A3		
Analysis	Sensitivity			Sensitivity	
Radiographic PD per		IRC		IRC	
Population		ITT		ITT	
Condition	Outcome	Date of Outcome	Outcome	Date of Outcome	
No post-baseline ATA	Censored	Date of randomization	Censored	Date of randomization	
Death	Event	Date of death	Event	Date of death	
Radiographic soft-tissue PD	Event	Date of PD	Event	Date of PD	
Clinical deterioration	NA	NA	NA	NA	
Any systemic non-protocol anti- cancer therapy (NPACT) received on or after randomization date	Event	Date of sNPACT	Censored	Date of last ATA on or prior to initiation of therapy	
Radiation (other than to bone)	Event	Date of radiation	Censored	Date of last ATA on or prior to radiation	
Surgery impacting soft tissue lesion	Event	Date of surgery	Censored	Date of last ATA on or prior to surgery	
≥ 2 consecutive missing scheduled ATA immediately prior to rPD or death	Censored	Date of last ATA prior to the missing assessments.	Event	Date of last ATA prior to the missing assessments.	
None of the above	Censored	Most recent of: the date of last ATA or randomization.	Censored	Most recent of: the date of last ATA or randomization.	

ATA=Adequate Tumor Assessment; PD=Progressive Disease; NA=Not Applicable; rPD = radiographic PD; RT=Radiotherapy Two or more missed scheduled ATA is operationally defined as >178 days without an evaluation

The median duration of PFS and its associated confidence interval (CI) will be estimated using the Kaplan-Meier product-limit method. The stratified and unstratified p-values are obtained from log-rank test. The stratified and unstratified hazard ratio (HR) and the associated 95% CI will be estimated using a Cox proportional- hazards model with treatment group as the independent variable. Stratification factors are those that were used for randomization.

Non-inferiority will be concluded if the upper 95% CI for the HR $_{(cabozantinib\ 60\ mg/140\ mg)}$ is less than the non-inferiority margin of 1.58.

A summary of concordance between the IRC and investigator determinations of rPD will also be provided.

7.2 Secondary Efficacy Endpoint

The secondary efficacy endpoint for this study is ORR as determined by the IRC per RECIST 1.1.

7.2.1 Definition

For each subject, best overall response (BOR) is defined as the best tumor assessment category as determined by IRC per RECIST 1.1 that occurs prior to any of the censoring events defined for the primary analysis of PFS as described in Section 7.1.3.

Tumor assessment categories are ranked as: confirmed complete response (CR), confirmed partial response (PR), stable disease (SD), progressive disease (PD) and not evaluable (NE).

To be classified as confirmed CR or confirmed PR, confirmation must have occurred on a subsequent visit that is ≥ 28 days after the response was first observed.

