#### **9.2.2.1 Definition**

The ORR is defined as the proportion of subjects with measurable disease at baseline who experience as best overall response of confirmed complete response (CR) or confirmed partial response (PR) per RECIST 1.1, which is confirmed at a subsequent visit  $\geq$  28 days later.

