# TIME POINT RESPONSE CRITERIA

Target Lesion Time Point Response (TPR)				
Complete Response (CR)	Disappearance of all target lesions. All pathological lymph nodes (whether target or non-target) must have reduction in short axis to < 10 mm.			
Partial Response (PR)	At least a 30% decrease in SoD of target lesions, taking as a reference the baseline SoD			
Stable Disease (SD)	Neither sufficient shrinkage to qualify for PR nor sufficient increase to qualify for PD.			
Progressive Disease (PD)	At least a 20% increase in the SoD of target lesions, taking as a reference the smallest (nadir) SoD since (and including) baseline. In addition to the relative increase of 20%, the SoD must also demonstrate an absolute increase of at least 5 mm.			
Not Applicable (NA)	No target lesion identified at baseline.			
Unable to Evaluate (UE)	One or more target lesions are not imaged and the remainder of the SoD compared with the nadir SoD does not meet the criterion for PD.			

SoD, baseline sum of diameters (longest for non-nodal lesions; short axis for nodal lesions)

If the target lesion for a subject meet the criteria for both PR and PD at a given time point, the target lesion response is PD.

If the nadir of SoD is 0 (ie, the subject had a prior target lesion CR), the reappearance of any prior target lesion to any degree constitutes PD.

Non-Target Lesion Time Point Response (TPR)				
Complete Response (CR)	Disappearance of all non-target lesions. All lymph nodes must be non-pathological in size (<10 mm short axis)			
Non-CR / Non-PD	Persistence of one or more non-target lesion(s).			
Progressive Disease (PD)	Unequivocal progression of non-target lesions. Unequivocal progression should normally trump target lesion status. It must be representative of overall disease status change, not a single lesion increase			
Not Applicable (NA)	No non-target lesions identified at screening			
Unable to Evaluate (UE)	One or more non-target lesions are not imaged and the remaining non-target lesions do not meet the criterion for PD.			

New Lesion Time Point Response (TPR)				

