Yes	Lesion present at follow-up visit either for the very first time or re-appearing (ie, lesion was present at baseline, disappeared at a follow-up visit and re-appeared later). On bone scan, a single new lesion may not be sufficient to qualify as PD. Confirmation should be obtained by performing CT or MRI of the area of concern to confirm ambiguous results of bone scan. Preferred method for confirmation is MRI.			
No	No new lesions present at follow-up.			
Unable to Evaluate (UE)	Subject not assessed or incompletely assessed for new lesions.			

Evaluation of Overall Time Point Response					
Target Lesion TPR	Non-target lesion TPR	New lesion TPR	Overall TPR		
CR	CR or NA	No	CR*		
CR	Non-CR/non-PD	No	PR*		
CR	UE	No	PR*		
PR	Any except PD	No	PR*		
SD	Any except PD	No	SD		
UE	Any except PD	No	UE		
PD	Any	No or Yes or UE	PD		
Any	PD	No or Yes or UE	PD		
Any	Any	Yes	PD**		
NA	CR	No	CR*		
NA	Non-CR/Non-PD	No	Non-CR/non-PD		
NA	UE	No	UE		
Any except PD	Any except PD	UE	UE		

CR, complete response; PR, partial response; SD, stable disease; PD, progressive disease, UE, unable to evaluate; NA, not applicable (no such lesions at screening); Any, CR, PR, SD, PD, NA, or UE.

The overall response at a given time point does not depend upon the overall response assigned at any prior or subsequent time point (ie, confirmation requirement are not considered when assigning time point responses).

\*Subjects with an overall response of CR or PR must have a repeat tumor assessment performed no less than 4 weeks after the criteria for response are first met. However, the presence or absence of confirmation is not considered when assigning a time point response.

\*\* If a lesion disappears and reappears at a subsequent time point it should continue to be measured. However, the patient's response at the point in time when the lesion reappears will depend upon the status of his/her other lesions. For example, if the patient's tumor had reached a CR status and the lesion reappeared, then the patient would be considered PD at the time of reappearance. In contrast, if the tumor status was a PR or SD and one lesion which had disappeared then reappears, its maximal diameter should be added to the sum of the remaining lesions for a calculated response.

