## **Best Overall Response**

Best overall response, incorporating confirmation requirements, will be derived during statistical analysis from the series of time point responses and need not be considered when assigning response at each time point.

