7.2.3 Primary Analysis

The key analysis of ORR will be based upon evaluations by the IRC and will include all subjects in the ITT population.

The following rules will be followed in determining the date of the objective response:

- If multiple assessment dates are associated with a tumor assessment visit with an overall response of CR or PR, the latest assessment date within the set will be chosen as the response date
- Single missing or not adequate scheduled tumor assessments will be ignored. No values will be imputed

- If missing/inadequate visits are immediately followed by progression or death, only evaluations before the missing/inadequate data will be considered in the determination of BOR
- If the missing/inadequate visits are immediately followed by an adequate assessment with an overall response of SD, PR or CR this will be deemed sufficient clinical evidence that progression did not occur during the period of missing data and the missing evaluations will be ignored. No values will be imputed

If the null hypothesis for the primary PFS analysis is rejected, then ORR between the two treatment groups will be compared using an unstratified two-sided chi-squared test at 5% level of significance. If a sufficient number of responders are observed, analysis using the Cochran-Mantel-Haenszel method to adjust for the stratification factors (see Section 2.4) will be generated.

Point estimates of ORR for each treatment arm, the difference in ORR between the two treatment arms, and associated confidence intervals will be provided. The odds ratio and its confidence intervals will also be shown. The 95% CIs for the point estimate will be calculated using exact methods. The 95% CIs for the difference in ORR between the two treatment arms and for the odds ratio will be calculated by asymptotic methods.

To provide a more detailed understanding of anti-tumor activity, baseline sum of target lesion diameter per IRC, the maximum tumor reduction since baseline in target lesions will be derived for those subjects who have baseline and at least one post-baseline measure. The maximum percent tumor reduction from baseline in target lesions for each arm will be displayed graphically using waterfall plots. For each subject, data from time points after the first date of any of the censoring events defined for the primary analysis of PFS as described in Section 7.1.3 will be excluded from the waterfall plots.

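### SAP 7.2.1 states no IRC-progression cut-off for best overall response, so read literally a CR or PR first seen or confirmed after IRC progression counts in ORR

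*SAP*

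**What the plan says.** **Response window.** SAP 7.2.1 limits best overall response (BOR) to the best IRC category "that occurs prior to any of the censoring events defined for the primary analysis of PFS". It ranks confirmed CR and confirmed PR above SD and PD, with no reference to their order in time. For a CR or PR, "confirmation must have occurred on a subsequent visit" at least 28 days later. Protocol 9.2.2.1 has the same requirement, "which is confirmed at a subsequent visit", and also names no progression limit.

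**Status of progression.** In SAP Table 3 (PFS-A1), the row "Radiographic soft-tissue PD" has the outcome Event. The outcome Censored belongs to other rows: no post-baseline adequate assessment, new systemic therapy, radiation other than to bone, soft-tissue surgery, two or more missed assessments before progression or death, and the residual category.

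**The one rule linked to progression.** Under SAP 7.2.3, when missing or inadequate visits come directly before progression or death, "only evaluations before the missing/inadequate data will be considered in the determination of BOR". The waterfall plots are cut at the PFS censoring events, with no mention of progression.

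**Protocol Appendix D.** "The overall response at a given time point does not depend upon the overall response assigned at any prior or subsequent time point". BOR "will be derived during statistical analysis from the series of time point responses".

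**ORR test.** SAP 7.2.3 compares ORR by an unstratified two-sided chi-squared test at 5%, only if PFS non-inferiority is shown. A CMH analysis by the stratification factor follows if there are enough responders; enough is not defined.

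**The concern.** The primary endpoint counts a subject with IRC progression as having failed on that date. Nothing in the BOR definition stops the same subject from becoming a confirmed responder on later scans. Appendix D does not settle the matter: it makes each time-point read independent of the others and leaves BOR to the statistical analysis, so the SAP has to supply the rule.

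Later scans can exist. Treatment beyond investigator progression is allowed. Scans go to the IRC until the later of 12 weeks after investigator progression or the decision to stop treatment (SAP 2.6). Because the investigator directs management, scanning can also continue after an IRC progression that the investigator did not call, and SAP 7.1.3 plans a summary of IRC and investigator concordance.

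At stake is who counts as a responder. Two programmers could follow the plan and classify the same subject differently, and settling it after unblinding would be a post hoc choice.

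**Working it through.** The plan gives no ORR power or expected response count, so there is no figure of its own to reproduce here.

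**1. Can the sequence occur under Appendix D?** PR needs a sum of diameters at least 30% below baseline. PD needs at least 20% and at least 5 mm above the nadir.

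| Sums (mm) | Reads | Check |
|---|---|---|
| 100, 65, 80, 68 | PR, PD, PR | 80 is +23.1% and +15 mm on nadir 65; 68 is +4.6% on nadir and 32% below baseline |
| 100, 75, 91, 69, 68 | SD, PD, PR, PR | 91 is +21.3% and +16 mm on nadir 75; 69 and 68 are 31% and 32% below baseline |

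With scans every 12 weeks the 28-day interval is met. Under 7.2.1 as written both are confirmed PR. In the first, confirmation comes after progression; in the second, the response itself does.

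**2. How narrow is it?** Appendix D says that if target lesions meet the "criteria for both PR and PD at a given time point, the target lesion response is PD", so real re-shrinkage is needed. With *f* the nadir as a fraction of baseline, and a nadir of at least 25 mm so that 20% is at least 5 mm, the smallest PD sum is 1.2*f*. The least further shrinkage from it that gives PR is

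1 − min(0.70, 1.2*f*) / (1.2*f*).

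- PR, PD, PR: any drop suffices if *f* ≤ 0.70/1.2 = 58.3%; 1 − 0.70/0.78 = 10.3% at *f* = 65%; 1 − 0.70/0.84 = 16.7% at 70%.
- SD, PD, PR, PR: 16.7% just above *f* = 70%; 1 − 0.70/0.90 = 22.2% at 75%; 1 − 0.70/1.20 = 41.7% at 100%.

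The subject must also have no new lesion, no non-target progression, and no new systemic therapy, non-bone radiation or soft-tissue surgery.

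**3. Effect on the test.** Assume 94 per arm. One subject is 1/94 = 1.06 ORR points. Pearson chi-squared, no continuity correction:

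- 14 vs 26 responders: pooled rate 40/188 = 0.2128; χ² = (12/94)² / (0.2128 × 0.7872 × 2/94) = 4.57; p = 0.0325.
- 15 vs 26: χ² = 3.77; p = 0.0520.
- With 26/94 fixed, only two of the 94 one-responder steps in the other arm cross 0.05: 14 to 15, and 38 to 39 (p = 0.0648 to 0.0462).
- From 18 vs 26 (p = 0.168), adding 1, 2, 3, 4 or 5 such responders to the higher arm gives p = 0.124, 0.090, 0.064, 0.045 or 0.031.

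The probability that removing one responder changes the conclusion is an exact sum over two independent Binomial(94, p) counts. The 140 mg ORR is 27.9% (prior Phase 3 study, Protocol 1.4.3.2.2); the 60 mg values are assumed.

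| 60 mg ORR | Removed from 60 mg arm | Removed from 140 mg arm |
|---|---|---|
| 27.9% | 2.0% | 2.0% |
| 20% | 6.3% | 4.7% |
| 15% | 7.7% | 6.5% |
| 10% | 3.5% | 3.5% |

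These hold given that one such subject exists and that PFS non-inferiority is met.

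**4. Stratified test (separate matter).** Assumed strata per arm are 36 M918T-positive (38% of 94, the share in Protocol 1.5.4), 49 negative and 9 unknown. That is 18 unknown in total, within the cap of 19. Stratum ORRs are assumed; power is for a 15-point overall drop with a common ratio; 400,000 simulated trials per row.

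| ORR positive/negative/unknown | Chi-squared size | CMH size | CMH power gain (points) |
|---|---|---|---|
| 28/28/28% | 4.9% | 5.0% | 0.1 |
| 40/20/28% | 4.5% | 5.0% | 0.9 |
| 50/15/28% | 3.6% | 5.0% | 3.1 |
| 50/12/28% | 3.1% | 4.9% | 3.5 |

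The 38% is of all enrolled subjects, while RET status was defined in only 65%; 38/65 = 58% of those determined. With 49/36/9 per arm the chi-squared size is 3.5 to 4.9% and the gain 0.1 to 3.9 points.

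**The case against.** The strongest reply is that the plan already assumes a progression limit. SAP 7.2.3 closes the window when progression follows missing visits, and treats a later SD, PR or CR as evidence that no progression occurred in the gap. That makes sense only if response is not expected after progression. It would be odd for progression after a missed visit to close the window while progression after an adequate visit left it open. This stands as evidence of intent, but intent is not a stated rule.

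Second, BOR is as the IRC determines it under RECIST 1.1, and IRC procedure sits in a charter that was not available. If the charter ends reads at IRC progression, the gap closes. This stands in full.

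Third, exposure is limited. SAP Table 1 shows that treatment beyond investigator progression came only with Amendment 4 (June 2018). Before that, treatment stopped at investigator progression and scanning ended at the earlier of 12 weeks later or new systemic therapy. SD, PD, PR, PR needs two scans after progression, hence treatment beyond it or an IRC progression not called on site. This also stands.

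On the test, the chi-squared comparison is prespecified consistently in the synopsis, Protocol 9.2.2.2 and SAP 7.2.3. CMH is only supportive, so its undefined condition cannot alter the gated conclusion, and ORR by M918T is reported descriptively in any case (SAP 7.6). All of that is right; it makes the change optional.

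**Conclusion.** The wording gap is real and small. As written, 7.2.1 admits a response first seen or confirmed after IRC progression, and only the case of progression after missing or inadequate visits is excluded. This is a clarification worth making, not a defect that threatens the trial.

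A reader might infer that ORR will be inflated, or tilted toward one arm. The documents do not support that: they give neither the number of such subjects nor their arm, 7.2.3 points to an intended limit, and the charter may supply it. A reader might also infer that the primary analysis is affected. It is not, since PFS takes IRC progression as an event. One such subject matters only in a borderline ORR result, with a probability of 2.0 to 7.7% under the assumed rates and 94 per arm.

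Nor is the chi-squared test wrong. It controls type I error. It is conservative if response differs by M918T (size down to about 3.1 to 3.5% in the most extreme case assumed), and a stratified test recovers 0.1 to 3.9 power points depending on the assumed strata.

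**What to change.** **Response window.** In SAP 7.2.1, state:

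> *BOR is derived from adequate IRC assessments up to and including first IRC progression and before any PFS censoring event, whichever is earlier. A CR or PR and its confirming assessment must both precede first IRC progression.*

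Apply the same cut to the waterfall plots in 7.2.3. If the charter already ends reads at IRC progression, cite that rule too. The cost is two sentences and no new data, made before unblinding by the route in SAP 4.8.

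**Stratified test, optional and separable.** Make CMH stratified by M918T as recorded in the randomization system the key ORR test, drop the condition on the number of responders, and keep the unstratified chi-squared test as supportive. Protocol 9.2.2.2 and the synopsis need matching wording. The downside is replacing a consistently prespecified test, so it should be done only before unblinding. The first change does not depend on it.
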